6.3.4 Storage and Stability

Vitamin D3 with calcium tablets are stored at room temperature 15°-30°C (59°-86°F), protect from light and moisture. They should be dispense in a tight, light-resistant container.

6.3.5 Dose Specifics

Placebo will be vitamin D with calcium tablets 10mcg/25mg tablet. See section 6.1 for dosing.

6.3.6 Preparation

No special preparation.

6.3.7 Administration

Take Vitamin D3 with calcium by mouth with meal or a glass of milk.

Take hydroxychloroquine sulfate by mouth, preferably with a meal or a glass of milk.

6.3.8 Contraindications:

Use of Vitamin D3 with calcium is contraindicated in patients with renal impairment, heart disease, kidney stones, arteriosclerosis, and individuals with hypercalcemia, hypervitaminosis D; gastrointestinal, liver, or biliary disease associated with malabsorption of vitamin D analogues and drugs that could have allergenic cross reactivity/hypersensitivity with Vitamin D3.

6.3.9 Availability

Commercially available as a tablet for oral administration. For the purposes of this study the tablet drug will be provided by Sanford Research and supplied in 10mcg/25mg tablets as placebo.

6.3.10 Side Effects

1. Renal: Impairment of renal function with polyuria, nocturia, polydipsia, hypercalcemia, reversible azotemia, hypertension, nephrocalcinosis, generalized vascular calcification, or irreversible renal insufficiency which may result in death
2. Central Nervous System (CNS): Mental retardation, disorientation, confusion
3. Soft Tissues: widespread calcification of the soft tissues, including the heart, blood vessels, renal tubules, and lungs
4. Skeletal: Bone demineralization (osteoporosis) in adults. Decline in the average rate of linear growth and increased mineralization of bones in infants and children (dwarfism), vague aches, stiffness, and weakness
5. Gastrointestinal: Nausea, anorexia, and constipation
6. Metabolic: Mild acidosis, anemia, and weight loss
7. Teratogenic effects: supraaortic stenosis, elfin facies, and mental retardation recorded in pregnant women with hypervitaminosis D

6.4 Participant Implications

1. If a participant vomits after taking their dose study drug it will be considered a missed dose and not retaken. The participant will resume with the next scheduled dose.
2. If the participant forgets to take a dose, that dose will not be made up and participant will resume with the next scheduled dose.
3. If the participant is unable to start the hydroxychloroquine / vitamin D with calcium in the morning on Day 1 due to delivery timing, the participant is allowed to initiate Day 1 with an evening dose.
4. Participants should have at least 8 hours between doses.

5. Participants will be instructed to inform the study coordinator of any medication changes while on the active phase of the study

6.5 Drug Inventory Records

Investigational Product Records at Investigational Site(s): It is the responsibility of the Investigator to ensure that a current record of investigational product disposition is maintained at each study site where investigational product is inventoried and disposed.

6.6 Measures to Minimize Bias: Randomization and Blinding

On enrollment day, the participant will be assigned a unique number (randomization number). The randomization number encodes the participant's assignment to hydroxychloroquine or placebo (vitamin D with calcium), according to the randomization schedule generated prior to the study by the Sanford Command Core. Each participant will be dispensed randomized study intervention, labeled with his/her unique randomization number, throughout the study.

In the event of a Quality Assurance audit, the auditor(s) will be allowed access to study intervention records at the site(s) to verify that randomization/dispensing has been done accurately.

6.7 Study Intervention Compliance

A pill diary will be given to each enrolled participant to document pill compliance.

6.8 Concomitant Therapy

- See inclusion and exclusion criteria for medications that are not allowed.
- No washout period is needed for hydroxychloroquine.
- Vaccines are allowed while on the study.

6.9 Intervention after the End of the Study

Participants who acquire COVID-19 while on study intervention as determined by a positive test indicating COVID-19 will be instructed to discontinue the study intervention by the study team. Participants will be unblinded and subsequent treatment will be at the discretion of their primary care physician or provider who ordered the COVID-19 testing.

7.0 Participant Discontinuation/Withdrawal

Participants may withdraw consent at any time for any reason or be withdrawn from the trial at the discretion of the investigator should any untoward effect occur. In addition, a participant may be withdrawn by the investigator if enrollment into the trial is inappropriate, the trial plan is violated, or for administrative and/or other safety reasons.

7.1 Discontinuation of Study Intervention:

A participant must be discontinued from the trial for any of the following reasons:

- The participant withdraws consent.
- Intercurrent illness that prevents further administration of treatment
- The participant has a confirmed positive pregnancy test
- The participant is lost to follow-up

At the discretion of the investigator for safety, behavioral, compliance, or administrative reasons.

For those participants who discontinue study intervention early, each participant will be followed for 30 days for acute adverse event monitoring.

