1.2 Schema

1.3 Schedule of Activities (SoA) Cohort A & B

This study consists of screening, enrollment and randomization, treatment, and follow-up. Follow-up will include evaluation of the treatment and subsequent infection, re-infection, adverse events, and long-term sequelae of treatment and/or infection. The detailed schedule of study procedures and assessments with the time intervals is shown in Table 1.

Table 1

| Procedure | Screening & Enrollment | | Treatment / Placebo Phase | | | | | Follow-up ^b | | |
|---|------------------------|----------------------------|---------------------------|-------|--------------------|-------|-------|------------------------|-------------------------------|----------------------|
| | Screening ^a | Enrollment / Randomization | Day 1 | Day 2 | Day 3 ^f | Day 4 | Day 5 | Day 14 (± 1 day) | Day 35 ^c (+3 days) | 12 Months (±30 days) |
| Informed Consent / HIPAA | X | | | | | | | | | |
| Inclusion/Exclusion | X | | | | | | | | | |
| Demographics | X | | | | | | | | | |
| Randomization | | X | | | | | | | | |
| Hydroxychloroquine / Placebo (Vitamin D with calcium) | | | X | X | X | X | X | | | |
| Patient Reported symptoms ^c | | | | | X | | X | X | X | |
| Adverse Event Assessment | | | | | X | | X | X | X | X |
| Outcomes ^d | | | | | | | | X | X | X |

a. Screening must be completed within 48 hours prior to study enrollment

b. Follow-up visits will consist of a phone call to the patient. Hydroxychloroquine and placebo patients will be followed.

c. Includes: patient reported temperature, cough, difficulty breathing, sore throat, chills, muscle pain, headache, new loss of taste or smell, and diarrhea.

d. Did the patient acquire COVID-19?

e. Day 35 should be at least 30 days (+3 days) post last dose of drug.

f. Day 3 and 5 AE assessment via phone call. (window ±1day)

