7.2 Participant Withdrawal from the Study

- A participant may withdraw from the study at any time at his/her own request, or may be withdrawn at any time at the discretion of the investigator for safety, behavioral, compliance, or administrative reasons.
- If the participant withdraws consent for disclosure of future information, any data collected be for that time may be retained.

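### Section 7.1 ends trial participation for some people who only stop study drug, while Table 1 schedules the infection outcome to 12 months with no exception for people off drug

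*Combined protocol and SAP*

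**What the plan says.** Section 7.1 is titled as a rule on discontinuing study intervention. Its text goes further: "A participant must be discontinued from the trial for any of the following reasons". Four reasons are listed: withdrawn consent, "Intercurrent illness that prevents further administration of treatment", a confirmed positive pregnancy test, and loss to follow-up. A line on investigator discretion follows. The section closes with "For those participants who discontinue study intervention early, each participant will be followed for 30 days for acute adverse event monitoring". It does not mention the infection outcome.

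Two neighbouring passages overlap with it. Section 7.0 says a participant may "be withdrawn from the trial at the discretion of the investigator should any untoward effect occur". Section 7.2, on withdrawal from the study, says a participant "may be withdrawn at any time at the discretion of the investigator for safety, behavioral, compliance, or administrative reasons".

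Table 1 (section 1.3) has an outcomes row marked at Day 14, Day 35 and 12 months. Footnote d defines it as "Did the patient acquire COVID-19", put as a question. Footnote b says of the follow-up visits: "Hydroxychloroquine and placebo patients will be followed". No footnote exempts people who have stopped tablets. Section 4.2 defines completing the study as completing all phases, including the 12-month visit.

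**The concern.** The heading and closing sentence of 7.1 concern stopping tablets; the sentence between them removes the participant from the trial. A site coordinator whose participant stops dosing on Day 3 because of an intercurrent illness finds an instruction to discontinue from the trial in 7.1 and three further outcome calls in Table 1. The protocol does not say which governs.

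The reasons at issue all arise after randomisation. In a trial of infection, an intercurrent illness may be related to the outcome, and stopping for safety may differ between hydroxychloroquine and placebo. Outcomes lost for these reasons could therefore be informatively missing. The 10% dropout allowance in section 9.2 protects the number analysed, not the comparability of the arms. An outcome call that was never made cannot be recovered at the analysis stage.

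**Working it through.** This is a conflict of wording, so the main check sets the passages side by side. The arithmetic only bounds the size.

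**1. Who is affected**

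| Reason for stopping | Effect on the outcome |
|---|---|
| Withdrawn consent | Properly ends data collection (10.7); no conflict |
| Lost to follow-up | Contact has failed; 7.3 adds a medical-record search |
| Positive COVID-19 test (6.1, 6.9) | Outcome already known |
| Illness preventing dosing | In conflict with Table 1 |
| Positive pregnancy test | In conflict with Table 1 |
| Investigator discretion (7.0, 7.1, 7.2) | In conflict with Table 1 |

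Only the last three rows matter, over a 5-day course.

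**2. Which time points are at risk**

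Early stopping means a last dose on Day 1 to 4. Counted strictly, last dose + 30 gives Day 31 to 34.

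- Day 14 (window 13 to 15) falls inside.
- Day 35 would start 1 to 4 days after the end on that count. However, 8.2.2 equates Day 35 with 30 days after the last dose, 8.3.1 collects acute events until Day 35 without excepting early stoppers, and footnote e says "Day 35 should be at least 30 days (+3 days) post last dose of drug". The 30 days in 7.1 are best read as the ordinary Day 35 contact.
- The 12-month call opens at 365 − 30 = Day 335. That is 335 − 35 = 300 days after Day 35, or 301 to 304 days after Day 34 to 31. Monitoring under 7.1 never reaches it.

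Up to Day 35, symptomatic COVID-19 should appear in the adverse event record (8.2.1, 8.2.2, 8.3.1). What could still be missed is an asymptomatic positive, and the structured outcome item if 7.1 is taken literally. No section says an adverse event record stands in for that item.

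**3. How many**

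The documents give no early-stopping rate. With 1356/2 = 678 per arm in Cohort A and 383/2 = 191.5 in Cohort B, assumed shares give:

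| Assumed share stopping early | A, per arm | B, per arm |
|---|---|---|
| 5% | 33.9 | 9.6 |
| 10% | 67.8 | 19.2 |
| 20% | 135.6 | 38.3 |

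At each assumed share these are upper limits for the 12-month outcome, since they treat every early stopper as discontinued under 7.1, including those whose positive test already supplies the outcome.

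**4. What counting early stoppers in their assigned arm costs**

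The plan's figures reproduce first. Exact power of the two-sided Fisher test at α = 0.0492 is 90.0% with 610 per arm (5% against 10%) and 90.0% with 172 per arm (15% against 30%). Dropout inflation also reproduces: 1220/0.9 = 1355.6, rounded up to 1356; 344/0.9 = 382.2, rounded up to 383.

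Now count everyone randomised and let active-arm stoppers carry full control risk, which is pessimistic. The active-arm risk is (1 − s)·p_T + s·p_C, where s is the assumed share stopping.

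| s | A: active risk | A: power (678 per arm) | B: active risk | B: power (191 active, 192 control) |
|---|---|---|---|---|
| 5% | 5.25% | 89.7% | 15.75% | 90.3% |
| 10% | 5.5% | 85.6% | 16.5% | 86.4% |
| 20% | 6.0% | 74.8% | 18.0% | 76.2% |

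In Cohort B at 10%, placing the odd participant in the active arm gives 87.7%. If stoppers keep half the benefit, the 10% case has active risks of 5.25% and 15.75%, hence 89.7% (A) and 90.3% (B). If a further 10% of outcomes are missing at random (610 and 172 per arm), the pessimistic 10% case falls to 81.4% and 81.7%. These figures price the dilution; they do not measure the harm from the wording conflict.

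**The case against.** The case for the protocol is substantial. Section 7.1 never says outcome calls stop, and its last sentence does not say that adverse event monitoring is all that continues. Table 1 is the operative schedule and covers both arms. Withdrawal from the study has its own section. The one statement that no further data are collected, in 10.7, is tied to withdrawn consent. All of this favours continued follow-up. It does not settle the matter: 10.7 is silent on investigator withdrawal, and 7.1 still orders discontinuation from the trial in mandatory terms.

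Four stronger readings are tempting, and the documents do not support them.

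- A reader might infer that early stoppers fall out of view 1 to 4 days before Day 35. Footnote e, 8.2.2 and 8.3.1 tie the 30 days to the Day 35 contact, so that gap is doubtful.
- A reader might infer a large loss of primary outcome data. That would need a 12-month primary time point. Sections 3 and 9 name none, the exposure is within the last 5 days, and the interim in 9.4 is triggered by 35-day follow-up. The unstated primary time point is a separate matter.
- A reader might take the power table as the damage done. It rests on assumed stopping shares and shows dilution only.
- A reader might conclude that the plan lacks an analysis population or a missing-data rule. Section 9.3 defers analysis detail to a SAP that is not in the supplied text, so absence cannot be asserted.

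**Conclusion.** The inconsistency is real and should be corrected. Section 7.1 taken literally conflicts with Table 1 and section 4.2 for participants who stop for intercurrent illness, pregnancy or investigator discretion. The clearest loss is their 12-month infection outcome. Up to Day 35 the loss is small: asymptomatic positives, and the structured Day 14 and Day 35 item if the wording is followed to the letter.

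The number affected is unknown, and neither the size nor the direction of any bias can be derived from the documents. The 5%, 10% and 20% shares are assumptions used only to show scale. Confidence is medium, because a site could reasonably read the protocol as continuing follow-up.

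**What to change.** Reconcile 7.0, 7.1, 7.2 and Table 1 so that stopping study drug does not by itself end the scheduled Day 14, Day 35 and 12-month outcome calls for anyone who has not withdrawn consent. Say which kinds of withdrawal do end data collection. The clinical reasons for stopping drug, and for investigator withdrawal, remain the sponsor's to set. Extend the medical-record outcome search in 7.3, where consent allows, to participants discontinued under 7.1.

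The cost is protocol wording and a few more telephone calls, mostly at 12 months. If early stoppers are counted in their assigned arm there is also some dilution. With 10% stopping (assumed), power would lie between 85.6% and 89.7% in Cohort A and between 86.4% and 90.3% in Cohort B (191 active, 192 control), depending on whether stoppers keep none or half of the benefit. The stated power is 90%. The analysis population, the handling of missing outcomes and any sensitivity analysis belong in the SAP and are not part of this change.

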7.2 Participant Withdrawal from the Study

- A participant may withdraw from the study at any time at his/her own request, or may be withdrawn at any time at the discretion of the investigator for safety, behavioral, compliance, or administrative reasons.
- If the participant withdraws consent for disclosure of future information, any data collected be for that time may be retained.

7.3 Lost To Follow Up

All reasonable efforts must be made to locate participants to determine and report their ongoing status. This includes follow-up with persons authorized by the participant.

Lost to follow-up is defined by:

- The inability to reach the participant after a minimum of two documented phone calls and
- Lack of response by participant to one certified mail letter.

All attempts should be documented in the participant medical record. Should the participant continue to be unreachable, he/she will be considered lost to follow up. Outcome information that is available via electronic medical records will be documented if available.

If it is determined that the participant has died, the site will use permissible local methods to obtain the date and cause of death.

8.0 Study Procedures and Safety Assessments

8.1 Administrative Procedures

8.1.1 Screening Procedures

All participants must agree to participate in the study prior to any study specific screening procedures being performed. Every participant shall be provided an Institutional Review Board (IRB)-approved informed consent to review and keep for his/her records.

Once consent has been documented, the site will assign the participant a screening number. A Screening Log of consented patients will be maintained at each site.

Screening evaluations will be used to determine the eligibility of the participant for study inclusion. All screening activities must be completed within 48 hours prior to study enrollment and include the following:

- Inclusion/Exclusion Criteria
- Demographics and Medical History

All screening evaluations must be completed and reviewed by the site investigator or healthcare licensed designee to confirm that potential participants meet all eligibility criteria. The study team will maintain a screening log to record details of all participants screened and to confirm eligibility or record reasons for screening failure, as applicable.

8.1.2 Informed Consent

A study team member must obtain documented consent from each potential participant prior to participating in a clinical trial. This study will utilize an electronic consent process based in REDCap, a CFR part 11 compliant research database. An electronic version of the informed consent form will be approved by the IRB prior to use. When a participant is contacted for enrollment into the study, an email containing a unique link will be generated by REDCap and sent to the patient while on the phone with a study team member. A password will be provided to the participant verbally over the phone that is required to access the informed consent. This provides confirmation of the identity of the participant. Once the informed consent form has successfully accessed, the study team member will allow a period of time of 1-4 hours for the participant to read the informed consent and formulate questions. The study team member will place another call with the participant and proceed to have an informed consent discussion, answering any questions the participant might have. If the participant is willing to participate in the study, he or she will proceed to provide an electronic signature using a mouse or their finger and save the document. This locks the document from any further changes. An email containing a copy of the signed informed consent form will be generated via REDCap and emailed to the participant. A PDF of the signed informed consent document will be saved in the participant's medical record as well as printed out for the study file.

A copy of the consent form will be automatically generated via REDCap and emailed to the participant before participation in the trial. The research team member who obtained consent will record the consenting process per their institutional guidelines.

The initial informed consent form, any subsequent revised written informed consent form and any written information provided to the participant must receive the IRB's approval in advance of use. The participant will be informed in a timely manner if new information becomes available that may be relevant to the participant's willingness to continue participation in the trial. The informed consent will adhere to IRB requirements, applicable laws and regulations.

8.1.3 Inclusion/Exclusion Criteria

All inclusion and exclusion criteria will be reviewed by the site Principal Investigator (PI) or licensed designee to ensure that the participant qualifies for the study.

8.1.4 Assignment of Screening Number

Consented participants will be assigned a screening number.

8.1.5 Enrollment

Once all screening procedures have been completed the site PI or licensed designee (RN, CNP, pharmacist, or physician) on the study team will review and acknowledge the inclusion/exclusion source document. If the potential participant is determined to be eligible, the study site will enroll the participant in appropriate cohort in the electronic data capture (EDC) and then randomized by the Sanford Command Core to the intervention assignment. Sites will be notified by email in real time the randomization confirmation. The site study team will maintain an enrollment log and the lead site will maintain a study-wide enrollment log. If the potential participant is not eligible and becomes a screen fail, the reason will be noted on the inclusion/exclusion in the EDC and filed in the study records.

8.1.6 Assignment of Study Participant Number

Participants will be assigned a participant study number at enrollment at the same time as randomization by the EDC. This number will be unique to this participant.

8.2 Clinical Procedures/Assessments

See Schedule of events for activities that need to be done at each visit.

8.2.1 Participant Reported Outcomes

Participant self-reported COVID-19 symptoms (temperature, cough, difficulty breathing, and sore throat) will be collected by the study team at time points outlined in the SoA. Participants will also be asked if they have or are

currently experiencing any other symptoms since starting the study intervention. These will be included in the adverse event monitoring.

8.2.2 Adverse Event (AE) Monitoring

The investigator or licensed designee (RN, CNP, pharmacist, or physician) on the study team will assess each participant to evaluate for potential new or worsening AEs as specified in the SoA and more frequently if clinically indicated. If participant reported symptoms are an AE, the event will be tracked as an AE.

Participants will be followed and accessed for acute AEs until day 35 (30 days after the last dose of study medication). AEs will be documented accordingly. Adverse events will also be assessed at the 12 month follow up visit.

8.3 Adverse events and Serious Adverse Events (SAE):

An AE is defined as any untoward or unfavorable medical occurrence in human participants, including any abnormal sign, symptom, or disease, temporally associated with the participant's participation in the research, whether considered related to the participant's participation in the research or not. AEs encompass both physical, psychological harms, and biochemical abnormalities. AEs may be reported by the participant, observed by the Investigator, or documented in medical records.

The site investigator and any licensed designees are responsible for detecting, documenting, and recording events that meet the definition of an AE or SAE and remain responsible for following up AEs that are serious, considered related to the study intervention or study procedures, or that caused the participant to discontinue the study treatment. The site investigator or licensed designee will evaluate all adverse events according to the National Cancer Institute (NCI) Common Terminology Criteria for Adverse Events (CTCAE) Version 5.0. Toxicities will be characterized in terms regarding grade (seriousness), causality/attribution (see section 8.3.2), and action taken with regard to trial intervention.

Any adverse event which changes CTCAE grade over the course of a given episode will have each change of grade recorded on the adverse event case report forms/worksheets.

If the adverse event meets any of the criteria below, it is regarded as a SAE:

- the event led to the death of the participant
- the event led to serious deterioration in the health of the participant, that either resulted in:
 - a life-threatening illness or injury
 - a permanent impairment of a body structure or a body function
 - in-patient or prolonged hospitalization

- an important medical event- defined as an event requiring medical or surgical intervention to prevent one of the outcomes listed above in this definition.

